12.1.2 Dose escalation

This study is designed to end if the rate of DLTs within 90 days from the start of treatment is 33% or higher. For each dose level cohorts, a total of seven to fifteen patients will be enrolled. If zero out of the first seven with 90 day follow-up, two or fewer out of the first nine with 90 day follow-up, three or fewer out of the first twelve with 90 day follow-up, or four or fewer out of the first fifteen of patients with 90 day follow-up experience a DLT as defined above, then the dose will escalate to the next dose level. If three or more of the first nine patients, four or more of the first twelve, or five or more of the first fifteen patients experience a DLT, then the MTD will be considered to have been exceeded. The MTD will be defined as the immediately previous lower dose level tolerated.

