6.9 Radiation Adverse Events

Adverse Events will be categorized and graded based primarily on the Common Toxicity Criteria for adverse events Version 3.0 (CTCAE version 3.0) with the exception of changes in pulmonary function tests (see section 6.9.4 below).

Radiotherapy should be interrupted for Grade 4 in-field toxicity and resumed when that toxicity has decreased to Grade \leq 2 as detailed below. If treatment is interrupted for > two weeks, the patient should be removed from study treatment.

6.9.1 Reversible or permanent alopecia, bone marrow toxicity, skin pigmentation, and esophagitis are expected side effects of radiation therapy. Radiation induced myocarditis or transverse myelitis rarely occur at doses lower than 50 Gy.

Radiographic evidence of radiation change and subsequent fibrosis of the lung will occur within lung volume receiving \geq 20 Gy, usually within the first six months after

initiation of treatment. It is essential to spare as much normal lung as possible in order to avoid symptomatic lung injury.

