6.9.3 Pneumonitis

Radiation pneumonitis is a subacute (weeks to months from treatment) inflammation of the end bronchioles and alveoli. Note: It is very important that a Radiation Oncologist participate in the care of the patient, as the clinical picture

may be very similar to acute bacterial pneumonia, with fatigue, fever, shortness of breath, nonproductive cough, and a pulmonary infiltrate on chest x-ray. The infiltrate on chest x-ray should include the area treated to high dose, but may extend outside of these regions. The infiltrates may be characteristically "geometric" corresponding to the radiation portal, but may also be ill defined.

Patients reporting symptoms as above will be promptly evaluated and treated. Mild radiation pneumonitis may be treated with nonsteroidal anti-inflammatory agents or steroid inhalers. More significant pneumonitis will be treated with systemic steroids, bronchodilators, and pulmonary toilet. Supra- and concurrent infections should be treated with antibiotics. Consideration of prophylaxis of opportunistic infections should be considered in immunocompromised patients.

It is unlikely that symptomatic pneumonitis will occur during the weeks radiation is actually delivered to the patients. However, if a patient experiences pneumonitis before completing therapy, therapy will be put on hold until symptoms resolve. At that point, a clinical decision whether to finish therapy will be made in conjunction with the treating physician in conjunction with [name], study Principal Investigator. When symptomatic pneumonitis resolves to grade 0, CTCAE, v. 3.0, the treating physician will contact [name] for a decision to continue or terminate protocol therapy.

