10.4 Criteria for Removal from Protocol Treatment

All reasons for discontinuation of treatment must be documented. All patients will be followed until death or 5 years post treatment (whichever time point comes first). If protocol treatment is discontinued for any reason other than death, follow up and data collection will continue as specified in the protocol.

10.4.1 Unacceptable toxicity.

10.4.2 A greater than two week delay in protocol treatment, as specified in Sections 6.0.

10.4.3 Development of intercurrent, non-cancer-related illnesses that prevent either continuation of therapy or regular follow-up.

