12.1.3 Waiting period

Dose escalation on this study should not occur until a sufficient waiting period has occurred after patients have been treated. A period of 90 days must pass in order to assess toxicity. If 90 days have transpired without DLT in each of the first seven (7) patients enrolled to a specific dose level, then dose escalation to the next level may proceed. Patients will continue to be enrolled to each dose level (up to a maximum of 15 patients) with ongoing assessment of those reaching 90 day follow-up so long as either criteria for defining the MTD (section 12.1.2) or criteria for further dose escalation is not reached. If fifteen patients are enrolled to a given dose level yet criteria for adequate follow-up are not reached in a representative sample of patients (section 12.1.2), further enrollment to the protocol will be suspended until adequate follow-up is reached.

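### The escalation counts set no minimum delivered course, so patients who stop radiotherapy early without a DLT count as tolerating the full dose

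*Combined protocol and SAP*

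**What the plan says.** Section 12.1.2 sets the target: "This study is designed to end if the rate of DLTs within 90 days from the start of treatment is 33% or higher". It then lists the counts that allow escalation, beginning "If zero out of the first seven with 90 day follow-up, two or fewer out of the first nine with 90 day follow-up", and the counts that mean the MTD has been exceeded: "If three or more of the first nine patients, four or more of the first twelve, or five or more of the first fifteen patients". Section 12.1.3 words the seven-patient rule by enrolment: "If 90 days have transpired without DLT in each of the first seven (7) patients enrolled to a specific dose level".

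The planned course is 15 fractions at every level (section 6.1.3). The protocol foresees that some patients will not complete it:

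- Section 10.4 lists three grounds for removal from treatment: "Unacceptable toxicity", a delay of more than two weeks, and intercurrent illness that prevents either therapy or regular follow-up.
- Section 6.9 states: "If treatment is interrupted for > two weeks, the patient should be removed from study treatment".
- Section 6.9.3 states: "if a patient experiences pneumonitis before completing therapy, therapy will be put on hold until symptoms resolve". It names no grade for this hold and leaves open whether therapy is then finished or terminated.

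Section 10.4 also settles what happens next: "If protocol treatment is discontinued for any reason other than death, follow up and data collection will continue as specified in the protocol".

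Sections 2.1.1 and 12.1.1 define a DLT as a listed grade 3 event, or any grade 4 or 5 event, judged probably or definitely related to treatment. Stopping radiotherapy is not in itself a DLT. No section of the documents defines a DLT-evaluable patient, sets a minimum number of fractions, or provides for replacing patients who do not complete the course.

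**The concern.** The primary question is whether each total dose is tolerated. A patient who stops early, stays in follow-up and has no DLT adds one to the denominator and nothing to the numerator. On the 60 Gy level, a patient who stops after six fractions because of an intercurrent illness has received 6 × 4 = 24 Gy. If that patient reaches day 90 without a DLT, the rule reads this as one more patient who tolerated 60 Gy.

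The affected group is specific: stops for intercurrent illness, for a delay of more than two weeks, for toxicity below DLT grade, for grade 3 toxicity outside the list, or for toxicity judged only possibly related. Seven to nine patients can decide a level, so one or two such patients can change the decision, and the consequence is that the next cohort receives a higher dose. Sections 2.1.1 and 12.1.1 themselves expect cardiopulmonary comorbidity and hospitalizations in this population.

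**Working it through.** **Inputs from the plan.** Stopping rate 33% (12.1.2). Escalate on 0/7, or on 2 or fewer of 9. Stop on 3 or more of 9, 4 or more of 12, or 5 or more of 15.

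**The plan's own figure.** 3/9 = 4/12 = 5/15 = 33.3%, so the boundaries reproduce the stated threshold. The largest passing counts are 2/9 = 22.2%, 3/12 = 25.0% and 4/15 = 26.7%. The plan states no error rate to reproduce.

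**Decision point.** Zero of seven always implies two or fewer of nine, and at nine every count either escalates or stops. So P(escalate) = P(X ≤ 2), with X binomial (9, p).

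At p = 1/3: (2/3)^9 + 9(1/3)(2/3)^8 + 36(1/3)^2(2/3)^7 = 0.377.

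**Assumptions.** The documents give no non-completion rate and no DLT risk for early stoppers. Let q be the share of counted patients who stop early, and f their DLT risk relative to a full course. With independent patients, the rate that the rule sees is p_e = p(1 − q) + p·f·q. For p = 1/3, q = 20%, f = 0.5: p_e = 0.2667 + 0.0333 = 0.300, and P(X ≤ 2) = 46.3%.

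P(2 or fewer DLTs of 9):

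| True full-course rate | f | q = 0 | q = 10% | q = 20% | q = 30% |
|---|---|---|---|---|---|
| 33.3% | 0.5 | 37.7% | 41.9% | 46.3% | 50.8% |
| 33.3% | 0 | 37.7% | 46.3% | 55.4% | 64.7% |
| 40% | 0.5 | 23.2% | 27.1% | 31.4% | 36.1% |
| 40% | 0 | 23.2% | 31.4% | 41.1% | 51.7% |
| 50% | 0.5 | 9.0% | 11.7% | 15.0% | 18.8% |
| 50% | 0 | 9.0% | 15.0% | 23.2% | 33.7% |

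**The seven-patient look alone.** P = (1 − p_e)^7. At 33.3% this is 5.9% with no early stoppers. At q = 10%, 20% and 30% it is 7.0%, 8.2% and 9.7% for f = 0.5, and 8.2%, 11.4% and 15.6% for f = 0.

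**Two direct readings of the counts.**

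- A passing 2/9 that includes three DLT-free early stoppers is 2/6 = 33.3% among full-course patients, which is the stopping rate.
- The one-sided 95% upper bound after 0/7 is 1 − 0.05^(1/7) = 34.8%. If two of the seven were early stoppers, 0/5 gives 1 − 0.05^(1/5) = 45.1%.

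**The case against.** The strongest case on the other side has four parts.

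**Most toxicity stops are already handled.** A reader might infer that any patient stopped for toxicity is scored as a success. The documents do not support that. Section 6.9 interrupts radiotherapy for grade 4 in-field toxicity. Section 6.9.2 does not treat esophagitis as a reason to interrupt while oral intake maintains hydration, and it discusses interruption at grade 3 or 4 or on hospitalization. Listed grade 3 events and all grade 4 or 5 events that are probably or definitely related count as DLTs however many fractions were given. Excluding possibly related events from the DLT count is deliberate and explained in 12.1.1. This part stands, and it confines the point to stops outside the DLT definition.

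**Pneumonitis during treatment is expected to be rare.** Section 6.9.3 says so and describes the condition as subacute. This stands too, so pneumonitis should not carry the argument. Intercurrent illness and long delays are listed separately and do not depend on it.

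**Zero DLT risk in early stoppers is a bound, not an expectation.** A patient removed with active toxicity remains under observation and can still progress to a DLT before day 90. This stands, which is why the half-risk rows are given. A reader might also take two DLTs plus three removals for toxicity as five of nine unable to complete. That does not follow: DLTs are counted to 90 days from the start of treatment, so the two DLT patients may have received every fraction.

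**Some early stoppers never enter the count, and under-delivery would be visible.** Patients whose illness also ends follow-up fall outside the 12.1.2 wording. Treatment breaks are documented (6.6), interim reports include treatment compliance (12.2), and a committee verifies DLTs (13.1). All true, but none of these defines the denominator. Early stoppers who reach day 90 still meet the only condition in 12.1.2.

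**Conclusion.** The point holds in its limited form. The rule as written gives a denominator place to a patient who stops radiotherapy early without a protocol-defined DLT. The documents do not expressly direct that such patients be counted; they set no condition that would leave them out. Stops for DLT-grade toxicity that is probably or definitely related are counted correctly.

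The direction is toward escalation whenever early stoppers have a lower DLT risk than full-course patients. The size cannot be fixed from the documents. At the plan's own stopping rate, the chance of escalating rises from 37.7% to between 41.9% and 64.7% over the range assumed here: 10% to 30% early stoppers, carrying half the risk or none, independent patients, decision at nine. The upper end rests on zero risk and should be read as a bound. The omission bears on the primary endpoint, but the remedy is a cheap improvement in wording and not a redesign.

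**What to change.** 1. In 12.1.2 and 12.1.3, base the 7/9/12/15 counts on DLT-evaluable patients: those with a DLT at any time after the first fraction, or those who received a pre-specified minimum of the assigned course and reached the 90-day assessment. The investigators set the minimum, before the data are seen. Use the same definition in both sections, in place of follow-up in one and enrolment in the other.
2. Replace every other patient who stops early without a DLT, whatever the reason, within the existing maximum of 15 per level. Wording the rule this way also covers stops for possibly related toxicity. A decision at nine leaves 15 − 9 = 6 places for replacements.
3. Reconcile 10.4.1, 6.9 and 6.9.3 with the DLT definition in 2.1.1 and 12.1.1, so that the plan states how a toxicity-driven discontinuation is classified. That classification is for the investigators to decide.
4. Report fractions delivered by dose level.

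The cost is an amendment to the wording, an occasional replacement patient within the cap, and a slightly slower escalation decision.

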12.1.3 Waiting period

Dose escalation on this study should not occur until a sufficient waiting period has occurred after patients have been treated. A period of 90 days must pass in order to assess toxicity. If 90 days have transpired without DLT in each of the first seven (7) patients enrolled to a specific dose level, then dose escalation to the next level may proceed. Patients will continue to be enrolled to each dose level (up to a maximum of 15 patients) with ongoing assessment of those reaching 90 day follow-up so long as either criteria for defining the MTD (section 12.1.2) or criteria for further dose escalation is not reached. If fifteen patients are enrolled to a given dose level yet criteria for adequate follow-up are not reached in a representative sample of patients (section 12.1.2), further enrollment to the protocol will be suspended until adequate follow-up is reached.

12.1.4 Other endpoints

A secondary endpoint is to evaluate local regional tumor control and overall survival by actuarial analysis.

12.2 Analysis Plan

Interim Reports: Interim reports will be prepared every six months until the results of the study are published or the study is closed. In general, the interim reports will contain information about patient accrual rate with projected completion dates of the trial, status of QA review and compliance rate of treatment per protocol, and the frequencies and severity of toxicity.

12.2.1 Estimation of Secondary Endpoints Related to the Efficacy: Cumulative incidence approach [23] will be used to estimate the failure rate for local-regional and distant failures. Kaplan-Meier method [24] will be used to estimate the overall survival rate.

13.0 Data Safety and Monitoring Plan

13.1 Data Safety Monitoring Committee and Institutional IRB reporting

A data safety monitoring committee including radiation oncologists not participating in this trial will be formed to review toxicity endpoints and efficacy data. The data safety monitoring committee will review and verify all reported DLTs. In particular, this committee will scrutinize the grading of adverse events and the attribution to therapy previously assigned by the investigators. This panel will have access to basic patient information so as to have the ability to critically review toxicity events. This study will use this committee to perform ongoing safety assessment at regular defined intervals defined in the statistics section of this protocol. Unexpected toxicities occurring between defined interim analyses points will be reported to the treating center's IRB and also to the University of Texas Southwestern IRB. Simmons Cancer Center Data Safety Monitoring Committee (DSMC) will review reported serious adverse events and contact Radiation Oncology DSMC for any discrepancies.

References

1. Jemal A, e.a., *Cancer Statistics 2008*. CA: a cancer journal for clinicians, 2008. **58**: p. 71-96.
2. Shields, T.W., *Surgical therapy for carcinoma of the lung*. Clin Chest Med, 1993. **14**(1): p. 121-47.
3. Perez, C.A., et al., *A prospective randomized study of various irradiation doses and fractionation schedules in the treatment of inoperable non-oat-cell carcinoma of the lung. Preliminary report by the Radiation Therapy Oncology Group*. Cancer, 1980. **45**(11): p. 2744-53.
4. Kong, F.M., et al., *High-dose radiation improved local tumor control and overall survival in patients with inoperable/unresectable non-small-cell lung cancer: long-term results of a radiation dose escalation study*. Int J Radiat Oncol Biol Phys, 2005. **63**(2): p. 324-33.
5. Lee, C.B., et al., *Late complications of high-dose (>/=66 Gy) thoracic conformal radiation therapy in combined modality trials in unresectable stage III non-small cell lung cancer*. J Thorac Oncol, 2009. **4**(1): p. 74-9.
6. Bradley, J., et al., *Toxicity and outcome results of RTOG 9311: a phase I-II dose-escalation study using three-dimensional conformal radiotherapy in patients with inoperable non-small-cell lung carcinoma*. Int J Radiat Oncol Biol Phys, 2005. **61**(2): p. 318-28.

Appendix II: Study Parameter Table

	Pre-Registration						During XRT		Follow-Up (months after therapy)		
	Within 8 weeks	Within 12 weeks	Within 3 days prior to XRT	Weekly	1 month	3 months	6 months	9 months	12 months	Q 4 months during year 2, after 2 years at the discretion of the investigator/institution	
History / Physical	X				X	X	X	X	X		X
Zubrod PS	X			X	X	X	X	X	X		X
Weight	X			X	X	X	X	X	X		X
Biopsy / cytology	X										
CT of Chest ¹	X					X	X	X	X		X
MRI Brain ²	X										
PFT's (including DLCO and FEV1)		X					X		X		
CBC w/ diff	X										
Serum or urine pregnancy test (if applicable)			X								
Informed consent	X										
Comorbidity index (Appendix V)		X									
Adverse event evaluation				X	X	X	X	X	X		X
Tumor response evaluation						X	X	X	X		X

¹preferably with IV contrast unless medically contraindicated

²CT if MRI medically contraindicated

APPENDIX III
ZUBROD PERFORMANCE SCALE

0	Fully active, able to carry on all predisease activities without restriction (Karnofsky 90-100).
1	Restricted in physically strenuous activity but ambulatory and able to carry work of a light or sedentary nature. For example, light housework, office work (Karnofsky 70-80).
2	Ambulatory and capable of all self-care but unable to carry out any work activities. Up and about more than 50% of waking hours (Karnofsky 50-60).
3	Capable of only limited self-care, confined to bed or chair 50% or more of waking hours (Karnofsky 30-40).
4	Completely disabled. Cannot carry on self-care. Totally confined to bed or (Karnofsky 10-20).
5	Death (Karnofsky 0).

KARNOFSKY PERFORMANCE SCALE

100	Normal; no complaints; no evidence of disease
90	Able to carry on normal activity; minor signs or symptoms of disease
80	Normal activity with effort; some sign or symptoms of disease
70	Cares for self; unable to carry on normal activity or do active work
60	Requires occasional assistance, but is able to care for most personal needs
50	Requires considerable assistance and frequent medical care
40	Disabled; requires special care and assistance
30	Severely disabled; hospitalization is indicated, although death not imminent
20	Very sick; hospitalization necessary; active support treatment is necessary
10	Moribund; fatal processes progressing rapidly
0	Dead

APPENDIX IV

AJCC STAGING SYSTEM **AJCC Staging, Lung, 6th Edition, 2002**

Primary Tumor (T)

TX Primary tumor cannot be assessed, or tumor proven by the presence of malignant cells in sputum or bronchial washings but not visualized by imaging or bronchoscopy.

T0 No evidence of primary tumor.

Tis Carcinoma *in situ*

T1 Tumor 3 cm or less in greatest dimension, surrounded by lung or visceral pleura, without bronchoscopic evidence of invasion more proximal than the lobar bronchus,* (i.e., not in the main bronchus)

T2 Tumor with any of the following features of size or extent: More than 3 cm in greatest dimension; Involves main bronchus, 2 cm or more distal to the carina; Invades the visceral pleura; Associated with atelectasis or obstructive pneumonitis that extends to the hilar region but does not involve the entire lung

T3 Tumor of any size that directly invades any of the following: chest wall (including superior sulcus tumors), diaphragm, mediastinal pleura, parietal pericardium; or tumor in the main bronchus less than 2 cm distal to the carina, but without involvement of the carina; or associated atelectasis or obstructive pneumonitis of the entire lung.

T4 Tumor of any size that invades any of the following: mediastinum, heart, great vessels, trachea, esophagus, vertebral body, carina; or separate tumor nodules in the same lobe; or tumor with a malignant pleural effusion.**

***Note:** The uncommon superficial tumor of any size with its invasive component limited to the bronchial wall, which may extend proximal to the main bronchus, is also classified T1.

****Note:** Most pleural effusions associated with lung cancer are due to tumor. However, there are a few patients in whom multiple cytopathologic examinations of pleural fluid are negative for tumor. In these cases, fluid is non-bloody and is not an exudate. Such patients may be further evaluated by videothoracoscopy (VATS) and direct pleural biopsies. When these elements and clinical judgment dictate that the effusion is not related to the tumor, the effusion should be excluded as a staging element and the patient should be staged T1, T2, or T3.

Regional Lymph Nodes (N)

NX Regional lymph nodes cannot be assessed.

N0 No regional lymph nodes metastasis

N1 Metastasis to ipsilateral peribronchial and/or ipsilateral hilar lymph nodes, and intrapulmonary nodes including involvement by direct extension of the primary tumor

N2 Metastasis to ipsilateral mediastinal and/or subcarinal lymph node(s)

N3 Metastasis to contralateral mediastinal, contralateral hilar, ipsilateral or contralateral scalene, or supraclavicular lymph node(s)

APPENDIX IV (continued)

AJCC STAGING SYSTEM AJCC Staging Lung, 6th Edition, 2002

Distant Metastasis (M)

MX Distant metastasis cannot be assessed
M0 No distant metastasis
M1 Distant metastasis present

Note: M1 includes separate tumor nodule(s) in a different lobe (ipsilateral or contralateral)

STAGE GROUPING

Occult Carcinoma	TX	N0	M0
Stage 0	Tis	N0	M0
Stage IA	T1	N0	M0
Stage IB	T2	N0	M0
Stage IIA	T1	N1	M0
Stage IIB	T2	N1	M0
	T3	N0	M0
Stage IIIA	T1	N2	M0
	T2	N2	M0
	T3	N1	M0
	T3	N2	M0
Stage IIIB	Any T	N3	M0
	T4	Any N	M0
Stage IV	Any T	Any N	M1

Appendix V: Comorbidity Scoring

Instructions for completing the CHARLSON COMORBIDITY INDEX (CCI):

1. Complete all patient information.
2. Follow the “Rules for Completing The Charlson Comorbidity Index” in this appendix.
3. Complete The Charlson Comorbidity Index” by noting “yes” or “no” for each disease.

Instructions for completing THE COMORBIDITY RECORDING SHEET:

1. Complete all patient information.
2. Extract all comorbidity elements you can identify and note them on the Recording Sheet.
Place the elements in the most appropriate category. Be comprehensive.
3. Include past surgeries, diseases, smoking history, and functional problems, such as incontinence or constipation.
4. For each condition include:
 - When (e.g., 6 months ago, 5 years ago, etc.);
 - Current symptoms;
 - Related treatment (e.g., surgery, stent placement, hearing aides, glasses, etc.);
 - Related laboratory values (e.g., CR, bilirubin);
 - Medications (scheduled/prn).
5. If a functional problem appears to be related to tumor or treatment, place **TR** after the diagnosis.
6. Specify as much as possible the dose/frequency of medications; the rater may use this information to rate the severity of a disease.
7. Leave the scoring column blank.

